9.2. SAMPLE SIZE ESTIMATION

Assessment of safety will be based on the assessment of AEs. To allow for at least a 95% chance of detecting an AE with a 10% incidence rate, a minimum sample size of 30 subjects per group (KPI-121 1% or prednisolone acetate 1%) is required. All statistical analyses will be performed using Statistical Analysis System (SAS) software.

9.3. LEVEL OF SIGNIFICANCE

Only descriptive analyses are planned.

9.4. PROCEDURE FOR ACCOUNTING FOR MISSING, UNUSED, OR SPURIOUS DATA

If more than 5% of data points are missing at the primary analysis time point (Day 15) in any treatment group, a tipping point analysis will be employed to assess the sensitivity of the results to the distribution of the allocation of treatment success and failure to the missing data points.

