5.1.5. Visit 4: Study Visit (Day 15 ± 2 days)

The following assessments/evaluations will be performed (**NOTE:** All ocular assessments must be performed in both eyes):

- Review use of any concomitant medications since the last visit
- Assess occurrence of any AEs since the last visit
- Perform (when obtainable):
 - Visual acuity assessed using the same method used at the screening visit
 - Signs of anterior ocular inflammation – cell and flare grading, corneal clarity, conjunctival injection, chemosis, hypopyon as well as and vitritis and wound integrity assessed using the same method used at the screening visit
 - Symptom assessment of anterior ocular inflammation – photophobia and lacrimation
 - IOP measurement
 - Modified Global Overall Assessment of Postoperative Inflammation
- Review dosing compliance/Dosing Diary.
- Collect initial investigational product Kit and dispense second Kit.
- Instruct parents/caregivers to return for Visit 5 on Day 29 ± 2 days. Remind them to bring the investigational product Kit and Dosing Diary with them.

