9.1.2. Evaluation of Efficacy

The efficacy and safety evaluations will be based on a single study eye, defined as the surgery eye, for each subject.

The primary analysis population will be the Intent-to-Treat (ITT) population, defined as all subjects randomized and with at least one post-baseline assessment. A subset of efficacy analyses will be repeated using data from those subjects who were randomized, completed 15 days \pm 2 days of investigational product use, had complete data at Visit 4 (Day 15 \pm 2 days), and did not have significant protocol deviations, the Per Protocol (PP) population. Rescued subjects will be included in the PP population if they did not have significant protocol deviations, however, these subjects will be considered treatment failures.

No inferential statistical analyses are planned. Data will be summarized using descriptive statistics only. Assessment of efficacy will be based primarily on the number and percentage of subjects in each treatment group with an anterior chamber cell grade of 0 at Visit 4 (Day 15 \pm 2 days) with no need for rescue medication through Visit 4 and, secondarily, on the Modified Global Overall Assessment of Postoperative Inflammation score of 0 at Visit 4 (Day 15 \pm 2 days) without receiving rescue medication prior to Visit 4.

The individual components of the Global Assessment score will also be evaluated (i.e., number and percentage of subjects in each treatment group in each score category at each visit).

The following scoring scale for anterior chamber cells will be used:

0 = No cells seen

1 = 1 - 5 cells

2 = 6 - 15 cells

3 = 16 - 30 cells

4 = greater than 30 cells

The following signs and symptoms scoring scales for inflammation will be used:

SIGNS	Grade 0	Grade 1	Grade 2	Grade 3	Grade 4
Anterior Chamber Cells	0 cells	1 - 5 cells	6 - 15 cells	16 - 30 cells	> 30 cells
Anterior Chamber Flare	Absent	Mild (trace to clearly noticeable, visible)	Moderate (without plastic aqueous humor)	Marked (with plastic aqueous humor)	Severe (with fibrin deposits and/or clots)
Corneal Clarity	Absent	Mild	Moderate	Severe	
Conjunctival Injection	Absent	Mild	Moderate	Severe	
Chemosis	Absent	Mild	Moderate	Severe	
Hypopyon	Absent	Mild	Moderate	Severe	
Vitritis	Absent	Mild	Moderate	Severe	
Wound Integrity	Absent	Mild	Moderate	Severe	
SYMPTOMS	Grade 0	Grade 1	Grade 2	Grade 3	
Photophobia	Absent	Mild	Moderate	Severe	
Lacrimation	Absent	Mild	Moderate	Severe	

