9.6. SUBJECTS TO BE INCLUDED IN THE ANALYSIS

The primary analysis population will be the Intent-to-Treat (ITT) population, defined as all randomized subjects with at least one post-randomization assessment. A subset of efficacy analyses will be repeated using data from those subjects who were randomized, completed 15 days \pm 2 days of investigational product use, had complete data at Visit 4 (Day 15 \pm 2 days), and did not have significant protocol deviations, the Per Protocol (PP)

population. Rescued subjects will be included in the PP population if they did not have significant protocol deviations.

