APPENDIX 3: ASSESSMENT OF SIGNS OF ANTERIOR OCULAR INFLAMMATION

Signs of anterior ocular inflammation will be assessed by slit lamp biomicroscopy, ophthalmoscopy or light examination depending on subject's tolerance and as determined by the Investigator. It is recommended that a table-top slit lamp be used if at all possible. The use of a portable slit lamp, ophthalmoscope or muscle light (transilluminator) should be reserved for subjects who cannot comply with the table-top slit lamp exam.

The same method will be used consistently for each subject (when possible).

The signs of anterior ocular inflammation will be performed at every study visit (when obtainable).

The following signs will be assessed:

Anterior Chamber Cells

- 0 = No cells seen
- 1 = 1 - 5 cells
- 2 = 6 - 15 cells
- 3 = 16 - 30 cells
- 4 = greater than 30 cells

Anterior Chamber Flare

- 0 = None
- 1 = Mild (trace to clearly noticeable, visible)
- 2 = Moderate (without plastic aqueous humor)
- 3 = Marked (with plastic aqueous humor)
- 4 = Severe (with fibrin deposits and/or clots)

Corneal Clarity

- 0 = Absent
- 1 = Mild
- 2 = Moderate
- 3 = Severe

Conjunctival Injection

- 0 = Absent
- 1 = Mild
- 2 = Moderate
- 3 = Severe

Chemosis

- 0 = Absent
- 1 = Mild
- 2 = Moderate
- 3 = Severe

Hypopyon

- 0 = Absent
- 1 = Mild
- 2 = Moderate
- 3 = Severe

Vitritis

- 0 = Absent
- 1 = Mild
- 2 = Moderate
- 3 = Severe

Wound Integrity (not assessed at Visit 1)

- 0 = Absent
- 1 = Mild
- 2 = Moderate
- 3 = Severe

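### Does the primary percentage need a stated rule for an unrescued ITT eye that has no Visit 4 cell grade?

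*Combined protocol and SAP*

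**What the plan says.** Sections 3.1 and 9.1.2 define success as cell grade 0 at Visit 4 with no earlier rescue. Section 9.1.2 reports it as "the number and percentage of subjects in each treatment group with an anterior chamber cell grade of 0 at Visit 4". The primary population is ITT, which Section 9.6 gives as "defined as all randomized subjects with at least one post-randomization assessment". A child seen at Visit 3 but not graded at Visit 4 therefore stays in ITT. Only the per-protocol population requires complete Visit 4 data.

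Section 5.1.5 and Appendix 3 make the grading of signs conditional on its being obtainable in the child. Sections 5.4 and 9.1.2 count rescued subjects as failures.

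The only text on missing data is Section 9.4. Its condition is "If more than 5% of data points are missing at the primary analysis time point (Day 15) in any treatment group", in which case "a tipping point analysis will be employed to assess the sensitivity of the results", and what it then examines is "the distribution of the allocation of treatment success and failure to the missing data points". On inference, Section 9.3 says: "Only descriptive analyses are planned". Section 9.5 refers to a statistical analysis plan without saying whether that means Section 9 or a separate document.

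**The concern.** These are children under four, and the plan itself expects that some cannot be graded. Failure is stated for rescued eyes only, and the denominator of the percentage is not spelled out. Two base cases therefore seem open for an unrescued, ungraded ITT eye: keep it in the denominator as a non-success, or leave it out. A tipping point analysis varies a base case but does not define one, and at or below 5% missing Section 9.4 asks for nothing.

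Because no test is planned, the two percentages are the whole primary efficacy result. If the rule were chosen after the data were seen, which arm looks better could depend on that choice. With no test or margin, the plan also does not say what result would count as tipped.

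**Working it through.** **The plan's own figure.** Section 9.2 gives 30 per group for at least a 95% chance of seeing an adverse event of 10% incidence. The chance of at least one event is 1 − 0.9^n: 0.9477 at n = 28, 0.9529 at n = 29 and 0.9576 at n = 30. The figure holds (29 is the smallest n that reaches 95%) and does not depend on the efficacy endpoint.

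**Inputs.** n = 30 ITT eyes per arm (Section 9.2, Figure 1) and a trigger of more than 5% missing in either arm (Section 9.4). The documents give no success rate and no expected number of ungraded eyes, so all counts below are assumed.

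**When the trigger fires.** 1/30 = 3.3%, not triggered. 2/30 = 6.7%, triggered. Section 9.4 is therefore silent only when each arm has at most one ungraded eye.

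**Effect of the open choice below the trigger.** With s successes and one eye missing, the arm is s/30 (non-success) or s/29 (left out). The gap is s/29 − s/30 = s/870.
- s = 17: 56.7% or 58.6%, a gap of 2.0 points.
- s = 29, the largest possible: 96.7% or 100%, a gap of 3.3 points.

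**Can the arms change order below the trigger?**
- One missing in each arm: the difference is (s1 − s2)/30 or (s1 − s2)/29, which always has the same sign. With 16 and 15 successes it is 3.3 or 3.4 points.
- One missing in arm 1 only: a reversal needs s1 < s2 and s1/29 > s2/30, that is 30·s1 > 29·s2. Since s1 ≤ s2 − 1, this needs 30·s2 − 30 > 29·s2, so s2 > 30. That is impossible with 30 eyes. A tie can be broken, by at most 3.3 points.
- Slightly unequal arms can flip, but only narrowly. For example, 14/29 against 15/31 is 48.3% against 48.4%; leaving out one eye in the first arm gives 14/28 = 50.0% against 48.4%. The difference goes from −0.1 to +1.6 points.

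**Above the trigger.** A reversal becomes possible from two missing eyes in one arm. With 15 and 16 successes and 2 against 0 missing, 15/30 − 16/30 = −3.3 points, while 15/28 − 16/30 = 53.6% − 53.3% = +0.2 points.

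A stronger example has 4 against 1 missing, with 16 and 17 successes:
- Left out: 16/26 − 17/29 = 61.5% − 58.6% = +2.9 points.
- Non-success: 16/30 − 17/30 = 53.3% − 56.7% = −3.3 points.
- Extreme allocations: 16/30 − 18/30 = −6.7 points, and 20/30 − 17/30 = +10.0 points.

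Here 4/30 = 13.3%, so Section 9.4 applies. Its analysis covers the 5 × 2 = 10 ways of assigning success and failure to the missing eyes. One of these is the all-failure case, which is the non-success result. The reader would see that the order is not robust.

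**What belongs to the open choice.** The extreme allocations span (m1 + m2)/30: 6.7 points with one missing eye per arm, 13.3 with two and 20.0 with three. Those spans come from the missing grades themselves and would remain under any prespecified base case, so they do not measure the cost of leaving the rule unstated.

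**Scale.** At 50% success in both arms, the 95% half-width of the difference is 1.96 × √(2 × 0.25/30) = 0.253, or 25.3 points. The 4-against-1 example swings 2.9 + 3.3 ≈ 6.2 points.

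**Visibility.** Section 9.1.2 reports the number with the percentage, so the denominator can be recovered: 16 with 61.5% means 26 eyes, and 16 with 53.3% means 30.

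**The case for a change.** The strongest case for a change is that non-success is an inference. The plan took care to call rescued eyes failures and said nothing of the kind for ungraded ones. Section 9.4 also speaks of giving success or failure to missing points, as though they began as neither. Appendix 4 goes further for Visit 2 pressure, which it makes mandatory with a fallback, while the primary sign at the primary visit is not mandatory. One sentence would settle the matter.

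Part of this stands. No sentence fixes the base case, an observed-case percentage is not ruled out, and the tipping criterion is not named. With heavier missingness the level of an arm can move noticeably: 14 successes with 6 ungraded is 46.7% (14/30) or 58.3% (14/24).

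The rest is weaker. A tipping point analysis reassigns missing outcomes whatever the base case, so its wording does not imply that those eyes are excluded. Requiring complete Visit 4 data for the per-protocol set alone suggests that ITT keeps ungraded eyes. Appendix 3 does give fallback examination methods for children who cannot manage the table-top slit lamp. Pressure at Visit 2 is mandatory because it is a randomization criterion (Section 4.3), which has no bearing on missing outcomes. Without a margin, an analyst can still tabulate the difference for every allocation and show where it changes sign.

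**Conclusion.** No change is called for. This is missing detail that analysts would fill sensibly: the endpoint, the ITT population and the per-protocol completeness condition, read together, make an ungraded, unrescued eye a non-success over all ITT eyes. The same reading serves the secondary endpoint.

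Below the 5% trigger the choice is worth at most 3.3 points in an arm and cannot reverse two arms of 30. Above it, the planned sensitivity analysis exposes any dependence on the missing grades. The plan as written produces no wrong result, and no test, margin or sample size rests on the choice. Extra tables of extreme allocations at any level of missingness, or a replacement for the tipping point analysis, would be preference. Writing the rule down would be a harmless clarification, and a separate analysis plan, if there is one, may already do so.

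The conclusion assumes about 30 ITT eyes per arm, a descriptive analysis, and counts reported with the percentages. It would need another look if a formal comparison were added.

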9.5. PROCEDURE FOR REPORTING DEVIATIONS FROM THE STATISTICAL PLAN

Any deviations from the statistical analysis plan will be described and a justification given in the final clinical study report.

9.6. SUBJECTS TO BE INCLUDED IN THE ANALYSIS

The primary analysis population will be the Intent-to-Treat (ITT) population, defined as all randomized subjects with at least one post-randomization assessment. A subset of efficacy analyses will be repeated using data from those subjects who were randomized, completed 15 days \pm 2 days of investigational product use, had complete data at Visit 4 (Day 15 \pm 2 days), and did not have significant protocol deviations, the Per Protocol (PP)

population. Rescued subjects will be included in the PP population if they did not have significant protocol deviations.

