	
The primary analysis population will be the Intent-to-Treat (ITT) population, defined as all subjects randomized and with at least one post-baseline assessment. A subset of efficacy analyses, the Per Protocol (PP) population, will be repeated using data from those subjects who were randomized, completed 15 days \pm 2 days of investigational product use, had complete data at Visit 4 (Day 15 \pm 2 days), and did not have significant protocol deviations. Rescued subjects will be included in the PP population if they did not have significant protocol deviations: however, these subjects will be considered treatment failures.
 
No inferential statistical analyses are planned. Data will be summarized using descriptive statistics only. Assessment of efficacy will be based primarily on the number and percentage of subjects in each treatment group with an anterior chamber cell grade of 0 at Visit 4 (Day 15 \pm 2 days) with no need for rescue medication through Visit 4 and, secondarily, on the Modified Global Overall Assessment of Postoperative Inflammation score of 0 at Visit 4 (Day 15 \pm 2 days) without receiving rescue medication prior to Visit 4.
 
The individual components of the Global Assessment score will also be evaluated (i.e., number and percentage of subjects in each treatment group in each score category at each visit).

Safety Evaluations:	
Assessment of AEs
 
Change from baseline to each post-surgery visit in ocular signs:
 
 • Visual Acuity • IOP Measurement • Dilated Ophthalmoscopy (at Visits 1 and 5 only) 
Assessment of safety will be based on the assessment of AEs. To allow for at least a 95% chance of detecting an AE with a 10% incidence rate, a minimum sample size of 30 subjects per group (KPI-121 1% or prednisolone acetate 1%) is required.

Eligibility Criteria:	
Inclusion Criteria:
 
At Visit 1, individuals of either gender and any race will be eligible for study participation if they:

1. Have informed consent and Health Insurance Portability and Accountability Act (HIPAA) authorization provided by parent or guardian prior to any study-related procedures.
2. Are 0-3 years of age (have not had their 4th birthday) as of the date of surgery.
3. Are candidates for routine, uncomplicated, cataract surgery
 - a. With or without capsulotomy and vitrectomy
 - b. With or without posterior chamber intraocular lens (IOL) implantation

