4.3. RANDOMIZATION CRITERIA

To qualify for randomization at Visit 2 (1st post-surgery assessment which may be later on the day of surgery or the following day), a subject must:

1. Have undergone routine, uncomplicated, cataract surgery, with or without capsulotomy and/or anterior vitrectomy and with or without posterior chamber IOL implantation and not combined with any other surgery.
2. Continue to meet inclusion/exclusion criteria with respect to current ocular and medical conditions and medications.
3. Continue to have IOP \leq 21 mmHg in both eyes.

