- Provide the Dosing Diary and review instructions for completion.
- The parent/guardian will administer the first dose of double-masked investigational product, in the study eye in the clinic under the supervision of a designated dosing coordinator.
- Study staff will assess the occurrence of any AEs after investigational product administration. **NOTE:** Signs and symptoms of inflammation typically seen after uncomplicated, cataract surgery will not be classified as AEs, but rather the condition under study.
- Schedule the subject to return to the clinic on Day 8 ± 2 days for Visit 3.
- Ask parent/guardian to bring the Dosing Diary with them to the next clinic visit.

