5.1.10. Early Termination Visit

In the event of study termination prior to Visit 6 but following Visit 2, every attempt will be made to ensure that the following will be performed/assessed (when obtainable) (**NOTE:** All ocular assessments must be performed in both eyes.):

- Review use of any concomitant medications since the last visit
- Assess occurrence of any AEs since the last visit
- Collect used and unused investigational product and dosing diary
- Perform (when obtainable):

- Visual acuity assessed using the same method used at the screening visit
- Signs of anterior ocular inflammation – cell and flare grading, corneal clarity, conjunctival injection, chemosis, hypopyon as well as and vitritis and wound integrity assessed using the same method used at the screening visit
- Symptom assessment of anterior ocular inflammation – photophobia and lacrimation
- IOP measurement
- Dilated ophthalmoscopy
- Modified Global Overall Assessment of Postoperative Inflammation

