APPENDIX 4: IOP MEASUREMENT

IOP measurements will be performed utilizing an Icare rebound tonometer, or similar tonometer according to the Investigator's standard procedure. All pressures will be recorded in mmHg.

IOP will be assessed at all study visits (when obtainable, except at Visit 2 when this assessment is required). If unable to obtain a valid measurement by tonometer at Visit 2, assessment by other means, as determined by the investigator, will be accepted.

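### Do the two wordings of the ITT set give two different primary analysis populations?

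*Combined protocol and SAP*

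**What the plan says.** The primary population is described in three places. The synopsis and section 9.1.2 use the same words: "defined as all subjects randomized and with at least one post-baseline assessment". Section 9.6 has "defined as all randomized subjects with at least one post-randomization assessment". None of them says which kind of assessment qualifies.

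Baseline has no formal definition. Its only other use is a synopsis safety heading, "Change from baseline to each post-surgery visit in ocular signs", which covers among other things "Dilated Ophthalmoscopy (at Visits 1 and 5 only").

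The order of events at Visit 2 matters:

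- Section 4.3 makes Visit 2 the first examination after surgery and the point of randomization: "To qualify for randomization at Visit 2 (1st post-surgery assessment".
- Appendix 4 makes intraocular pressure compulsory there: "IOP will be assessed at all study visits (when obtainable, except at Visit 2 when this assessment is required").
- In 5.1.3 the eye examination comes before randomization. Dispensing and the supervised first dose follow, and then: "Study staff will assess the occurrence of any AEs after investigational product administration".
- Under 5.1.10, for a child who leaves after Visit 2, "every attempt will be made to ensure that the following will be performed/assessed (when obtainable").

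Section 9.4 calls for a tipping point analysis when more than 5% of Day 15 data points are missing in any treatment group. Section 9.3 limits the trial to descriptive analysis.

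**The concern.** Taken at face value, the two wordings could define two sets. For dilated ophthalmoscopy, done only at Visits 1 and 5, baseline can only be Visit 1. If that meaning is carried to the ITT wording, the Visit 2 examination is already post-baseline. Every randomized child has one, so the synopsis and 9.1.2 describe all randomized children. Section 9.6 looks narrower, because the Visit 2 examination precedes randomization and the next scheduled eye examination is Visit 3.

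Two things would then be at stake. The first is the denominator of the primary percentage, which matters because in a descriptive trial that percentage is the efficacy result. The second is the safeguard in 9.4: a child outside the ITT set is not a missing value within it, so the narrower set could remove early losses and also keep the tipping point analysis from running.

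Two neighbouring silences add to the impression. The plan does not state how a missing Visit 4 cell grade counts for a child who was not rescued. Section 9.4 does not give the base of the 5%, or say what tips when there is no test.

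**Working it through.** **The plan's own figure.** Section 9.2 wants at least a 95% chance of seeing an adverse event of 10% incidence and states 30 per group. The chance is 1 − 0.9^n: 0.9477 at n = 28, 0.9529 at n = 29 and 0.9576 at n = 30. The smallest n is 29, so 30 is confirmed. The ITT definition plays no part in it.

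**The readings side by side.** Two words are open: baseline (Visit 1, or the pre-dose values at Visit 2) and assessment (any, or efficacy only).

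| Baseline | Assessment in 9.6 | Do the sets differ? |
|---|---|---|
| Visit 2, pre-dose | any | practically no |
| Visit 2, pre-dose | efficacy only, read so in all three places | practically no |
| Visit 1 | any | only for a child randomized, not dosed or checked at Visit 2, and never seen again |
| Visit 1 | efficacy only | yes, for any child not examined after Visit 2 |

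Only the last row has a material effect, and it needs a word that 9.6 does not contain. The plan's own usage points the other way. The assessment lists in the synopsis and 3.4 include adverse events. Appendix 1 has an adverse event assessment row marked at Visit 2, with a footnote starting it at the first instillation. Section 5.1.3 requires the check after the dose given in clinic.

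The last row is also uneven. The argument that every randomized child has something post-baseline leans on the compulsory pressure reading. Section 8.1 lists that reading as a safety parameter next to adverse events. Counting one under the synopsis wording and refusing the other under 9.6 applies two standards. (The Visit 2 sign examination, where obtainable, is an efficacy assessment and would carry most children in any case.)

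**Size in the last row.** Inputs: 30 per arm (section 9.2 and Figure 1); m children missing at Day 15, of whom k were never examined after Visit 2; 18 successes. The values of m, k and 18 are assumptions; the plan gives none.

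- Missing fraction, all randomized: m/30. Under the narrow 9.6 set: (m − k)/(30 − k), if the 5% is taken of ITT.
- The trigger is passed above 0.05 × 30 = 1.5 children, so at 2 or more.
- m = 2, k = 1: 2/30 = 6.67% (runs) against 1/29 = 3.45% (does not).
- m = 2, k = 2: 6.67% (runs) against 0/28 = 0% (does not).
- m = 3, k = 1: 3/30 = 10.0% against 2/29 = 6.90% (runs under both).
- m = 3, k = 2: 10.0% (runs) against 1/28 = 3.57% (does not).
- Success percentage: 18/30 = 60.0%, 18/29 = 62.1%, 18/28 = 64.3%.

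**Size on the plan as written.** With the Day 1 check counted, a dosed child lost afterwards stays in the set and counts as missing. Two such losses give 2/30 = 6.67%, and 9.4 runs. Allocating those two values spans 18/30 = 60.0% to 20/30 = 66.7%. One loss gives 1/30 = 3.33%, and 9.4 does not run. The most that handling of that one value can do is 18/30 = 60.0%, 18/29 = 62.1% or 19/30 = 63.3%.

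**The case for a change.** The best case for a change is that the text does disagree with itself about its primary population, and that a plan should settle this before the treatment code is opened. An analyst used to efficacy sets might read 9.6 as requiring a post-dose efficacy examination. In children under 4, where examinations are done only when obtainable, some loss is foreseeable. The narrow reading would hide exactly the losses that 9.4 is there to expose.

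Part of this stands. The wordings differ, baseline is undefined, and under one combination of readings a single excluded child can carry an arm from above 5% to below it. Three things limit it:

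- That combination takes baseline from one loose safety heading, which promises change at each post-surgery visit for a sign not measured at each one. It also leaves the synopsis condition with nothing to exclude. Reading baseline as the pre-dose Visit 2 values gives the condition some work to do and agrees with 9.6.
- Children leave the 9.4 trigger only if its base is ITT. Section 9.4 speaks of treatment groups and does not mention ITT.
- Losing a child from every later examination is made less likely by the attempted Early Termination visit and by the rule in 5.4 that rescued children stay under follow-up to Visit 6.

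The silences in 9.4 are real but ordinary. Success requires an observed grade of 0, only the per-protocol set requires complete Visit 4 data, and 9.4 allocates missing values to success or failure. Together these lead an analyst to keep such a child in the denominator and show what the missing value could do.

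**Conclusion.** No change follows. The difference between the synopsis and 9.1.2 on one side and 9.6 on the other is a clerical slip: with assessment used as the plan uses it, both wordings keep essentially every dosed child. The residual difference is a child randomized at Visit 2, not dosed or checked there, and never seen again. Randomization and the supervised first dose belong to the same visit, so this should be rare.

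The effects of about 2 percentage points per child, and of a 9.4 trigger that fails to fire, arise only if baseline means Visit 1, 9.6 means efficacy assessments only and, for the trigger, the 5% is taken of ITT. They also rest on assumed counts; the plan gives no rate of early loss.

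The unwritten details in 9.4 are ones that analysts fill sensibly in a trial with no test or margin and with a tipping point analysis already planned. Rewording would make the text tidier, but no gain to the trial's conclusions has been shown. The conclusion assumes that the post-dose adverse event check counts as an assessment, that first doses are given in clinic as 5.1.3 sets out, and that each arm has about 30 children.
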